Seropositivity and Adverse Birth Events in Migrants From Bilharzia-endemic Areas

NCT03158298

Date: 2.10.2015

Study Protocol and Statistical Analysis Plan

Project Objectives

The aim of the proposed research project is to study the impact of Schistosomiasis on adverse birth outcomes (ABO) (as defined by low birth weight) in migrants to Europe from *Schistosoma*-endemic areas. This project will examine if pregnancies in *Schistosoma*-infected women are associated with reduced birth weight, premature delivery and stillbirth of the exposed infants.

Purpose:

To examine the association between Schistosomiasis seropositivity and adverse pregnancy outcomes. Hypothesis: In pregnant women from endemic areas for schistosomiasis, positive *Schistosoma* serology is associated with reduced birth weight in the infant.

Rationale:

Schistosomiasis is a widespread helminthic infection, with an estimated 249 million people in 78 countries requiring preventive antiparasitic therapy each year. This infection has a significant association with morbidity worldwide. In most endemic areas long lasting urogenital schistosomiasis constitutes a risk factor for bladder cancer^{1,2}. In a study performed in Malawi the reproductive tract was affected in more than 60% of women who excreted *S. haematobium* ova in urine³. Transplacental transmission has not been observed, but schistosomiasis of the pregnant uterus has been reported and placental schistosomiasis has been associated with stillbirth^{4,5}. Placental schistosomiasis (i.e. detection of schistosomiasis eggs in placental tissue) has been reported only occasionally, but to our knowledge no study has prospectively examined this^{5,10,11}. Schistosomiasis has been postulated to be associated with premature delivery and low birth weight⁶⁻⁹, but further data are required.

Migration to the EU was estimated at 1.7 million people in 2012. Migrants were predominantly from Africa and Asia (25 %, respectively)¹². In these areas schistosomiasis has an estimated prevalence of 10-20%¹³⁻¹⁵. Therefore there are a large number of migrants from schistosomiasis-endemic areas entering Europe and accessing health care. Many of these migrants are unaware of helminthic infections they may have been exposed to, and the potential outcomes these infections may have.

Methodology:

A prospectively ascertained cross-sectional study using mother-child data pairs will be conducted in pregnant migrants attending for medical care in Rome, Dublin and Jena from *Schistosoma*-endemic areas.

Inclusion criteria: Pregnant women >18 years originally from endemic countries and areas (as defined by WHO) who give written informed consent to the study.

Exclusion criteria: Placental pathology due to any cause and any other medical condition affecting fetal growth.

Primary analysis: Association between *Schistosoma* seropositivity and birth weight (details below).

Secondary analyses: Association between *Schistosoma* seropositivity and intrauterine growth restriction (IUGR)¹⁶ (defined as birth weight below the 10th birth weight percentile), stillbirth and premature delivery.

Assessments: A questionnaire (see below) will be completed on each subject including demographics, age, medical history, and history of *Schistosoma* infection. Data concerning the primary (birth weight percentiles) and secondary outcomes (intrauterine growth restriction, stillbirth and premature delivery) will be collected. The necessary values consist of gestational age, weight and sex of the new born. Gestational age will be either determined by ultrasound or by calculation of the last menstrual period. *Schistosoma*-specific antibody detection will be performed locally on serum by a commercially available *in vitro* diagnostics certified qualitative ELISA test.

Questionnaires: Known categorical variables that are affecting fetal growth are smoking, alcohol, diabetes, baby gender, ethnic origin and parity. Known continuous variables are birth weight, gestational length, maternal height and weight²⁴. The country of origin will provide the ethnic origin more precisely. Medical conditions and concomitant medication of the mother are documented. Relevant laboratory parameters - if available from the clinical routine - will be added to the dataset: Hemoglobin, Eosinophils, HIV-status and Hepatitis B and C status (Hbs-Ag, Anti-HCV). Factors resulting from exposition that can influence serological results are: previous history of Bilharzia, previous treatment and time since previous treatment of Bilharzia, fresh water contacts in the area of origin or on the way to Europe, time since migration to Europe and the type of travel to Europe. Data will be collected with a standardized case report form (eCRF) and will be pseudonymised at source. Property transfer for material (placenta and serum) is part of the questionnaire.

Sample size estimates: We estimated that n=200 mother-newborn pairs can be realistically ascertained within the funding period in the participating study centers in Germany, Italy and Ireland. Furthermore,

we expect 20% of the serologic tested samples to be positive (i.e. $n_{\text{positive}} \approx 40$; $n_{\text{negative}} \approx 160$ based on previous literature¹³⁻¹⁵). Intrauterine growth restriction (IUGR) is defined by birth weight below the 10th percentile of the reference curves. It occurs in 5-10% of all pregnancies and can be compared across multi-ethnic populations^{16,18-20}. We hypothesize that serologic positivity will result in reduced birth weight. In the given setting of our project, a study with $n=200$ mother-newborn pairs has a power of 80% to detect a standardized mean difference in birth weight percentiles of 0.5 (in units of standard deviations of a standard normal distribution; a moderate effect according to Cohen) at a significance level $\alpha=5\%$ (two-sided; planning by Student's test for 4:1 sample size ratio; nQuery 3.0).

Statistical analysis: The primary analysis will be a Mann-Whitney-Wilcoxon test to compare birth weight percentile distributions between the two groups of newborns born to seronegative and seropositive mothers (at a two-sided significance level $\alpha=5\%$). We will also evaluate known factors that influence birth weight (see above in paragraph questionnaire) in univariate regression models for the birth weight percentile outcome. Single confounders with a potential impact on the relationship between serum-status and birth weight percentile will be included in multiple linear regression models based on the univariate results ($p<0.2$). Similar to these sensitivity analyses, all other inferential statistics to compare the secondary outcomes between the two groups of negative and serum-positive newborns will be done exploratively using Fishers exact tests for the dichotomous variables (IUGR, stillbirth and premature delivery) while reporting the respective effects size estimates and 95% confidence intervals.

References

1. Richter J RA. Schistosomiasis oder Bilharziose. In: Löscher T. BGD, ed. Tropenmedizin in Klinik und Praxis. 4 ed. Stuttgart & New York 2010:676-703.
5. Bittencourt AL, Cardoso de Almeida MA, Lunes MA, Casulari da Motta LD. Placental involvement in schistosomiasis mansoni. Report of four cases. The American journal of tropical medicine and hygiene 1980;29:571-5.
7. Olds GR. Administration of praziquantel to pregnant and lactating women. Acta Trop 2003;86:185-95.
9. Siza JE. Risk factors associated with low birth weight of neonates among pregnant women attending a referral hospital in northern Tanzania. Tanzania journal of health research 2008;10:1-8.

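### The variable list cited for the birth weight percentile regressions includes birth weight, a component of that outcome, and no sentence removes it (minor; sensitivity analyses only)

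*Combined protocol and SAP*

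**What the plan says.** All references are to the combined protocol and SAP.

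- **Outcome.** Assessments makes the percentile the primary outcome: "Data concerning the primary (birth weight percentiles) and secondary outcomes (intrauterine growth restriction, stillbirth and premature delivery) will be collected". It then names what the percentile is built from: "The necessary values consist of gestational age, weight and sex of the new born".
- **Candidate factors.** Statistical analysis says the plan will evaluate "known factors that influence birth weight (see above in paragraph questionnaire) in univariate regression models for the birth weight percentile outcome". The cross-reference leads to Questionnaires, which has two lists. The categorical one reads "Known categorical variables that are affecting fetal growth are smoking, alcohol, diabetes, baby gender, ethnic origin and parity". The continuous one reads "Known continuous variables are birth weight, gestational length, maternal height and weight".
- **Entry into the multiple model.** Eligible variables are described as "Single confounders with a potential impact on the relationship between serum-status and birth weight percentile". The plan's rule is that such variables "will be included in multiple linear regression models based on the univariate results", with a threshold of p<0.2.
- **Status.** The next sentence opens with "Similar to these sensitivity analyses", so the regressions support the primary Mann-Whitney-Wilcoxon test, which has no covariates.

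**The concern.** A variable that enters the calculation of the outcome stands on the list from which that outcome's predictors are to be drawn. Followed step by step, the text regresses birth weight percentile on birth weight, finds a very small p-value and carries birth weight into the multiple model. The serology coefficient then compares seropositive and seronegative mothers whose babies weigh the same. What remains of the percentile at a fixed weight mostly reflects gestational age, so the coefficient no longer measures the growth deficit that the study is about.

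The comparison is not randomised and the primary test is unadjusted. These regressions are therefore the only planned statistical adjustment for smoking, parity, maternal size and similar factors, and readers will use them to judge whether a primary result could be confounding. With birth weight in the model, a real deficit could be misread as largely explained by maternal factors.

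**Working it through.** **1. The plan's own figure.** Sample size estimates gives 40 v 160, a difference of 0.5 SD and two-sided alpha 5% by Student's test. Noncentrality = 0.5/√(1/40 + 1/160) = 2.83 on 198 degrees of freedom, which gives a power of 80.4%. The stated 80% reproduces. It involves no covariates, so this point does not touch it.

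**2. The planned effect in percentile points.** If the z-score behind the percentile is N(0,1) in seronegatives and N(-0.5,1) in seropositives, the difference in mean percentile is 100 × [Φ(-0.5/√2) - 0.5] = -13.8 points.

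**3. Does the screen remove birth weight?** In two separate simulations, with different assumptions, birth weight passed p<0.2 in 100% of runs. The numerical rule alone would not take it out.

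**4. Why the coefficient shrinks.** Write birth weight as an expected weight for gestation and sex plus w × z, where w is the weight SD at fixed gestation. Treating w as constant and gestation as equal in both groups, the share of the serology effect (z scale) that survives adjustment for birth weight is about

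k = V/(V + w²), where V = (gain per week × gestation SD)² + (sex difference)²/4.

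Assumed, because the documents give none of these: mean 3300 g, CV 13% (w = 0.13 × 3300 = 429 g, w² = 184,041), 150 g/week, sex difference 120 g (120²/4 = 3,600).

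| Gestation SD (weeks) | V | k | -0.5 × k | Simulated coefficient |
|---|---|---|---|---|
| 1.2 | 180² + 3,600 = 36,000 | 0.16 | -0.08 SD | -0.08 SD |
| 1.8 | 270² + 3,600 = 76,500 | 0.29 | -0.15 SD | -0.14 SD |
| 2.5 | 375² + 3,600 = 144,225 | 0.44 | -0.22 SD | -0.23 SD |

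Without birth weight the simulated coefficient was -0.50 SD. With birth weight, gestational length and sex all forced in, it was essentially zero (-0.01 to 0.00 SD), because the three together almost determine the percentile.

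**5. Wider range, applying the p<0.2 rule.** A grid of 54 settings was run with 2,000 simulated studies each: CV 11, 13 and 15%; gestation SD 1.2, 1.4, 1.8, 2.0, 2.5 and 3.0 weeks; gain 120, 150 and 200 g/week; 40 v 160; true effect 0.5 SD. Candidates were birth weight, gestational age, sex, maternal height and smoking. Results are on the percentile scale.

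| Model | Serology coefficient (points) | Significant in |
|---|---|---|
| Maternal factors only | -13.4 to -13.9 | 79-84% |
| p<0.2 rule without birth weight (gestation gap 0-1 week) | -13.0 to -13.8 | 74-83% |
| p<0.2 rule with birth weight, equal gestation | -0.9 to -7.9 | 6-52% |

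With birth weight available, 6-58% of the effect is kept, and less than half in 50 of the 54 settings. If gestational length is always left out, up to 72% is kept. The simulation assumes that the reference curves fit this population.

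**6. Sign of the coefficient.** At equal gestation it stayed negative throughout the grid. A change of sign needs seropositive women to deliver earlier as well. By the approximation in step 4 at gestation SD 1.8, the birth weight slope is 429/260,541 = 0.00165 SD per g. A gap of d weeks then gives -0.5 + 0.00165 × (214.5 + 150d), which is zero at d of about 0.6. When gestational length also enters, the reversal goes: at CV 13%, SD 1.4, 150 g/week and a 1-week gap, the coefficient is -0.6 points with it in and +4.5 with it out.

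**The case against.** The strongest reply is that the plan would not enter birth weight. Statistical analysis limits the candidates twice, to factors that influence birth weight and then to confounders of the serology-percentile relationship. Birth weight does not influence itself, and a measurement from which the outcome is computed is not a confounder of it. Questionnaires is a data-collection paragraph that also covers items such as type of travel and sample ownership, so some selection is intended. Birth weight has to be recorded there anyway to compute the percentile, and the phrase about fetal growth is attached to the categorical list, extending to the continuous one only by inference.

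Most of this stands. It rules out the reading that the plan sets out to adjust for birth weight; the documents state no such intention. It does not dispose of the point. The cross-reference leads to a list that names birth weight, nothing takes it off, and the only numerical criterion would keep it. Gestational length and newborn sex, also components of the percentile, stand in the same lists, so these were not visibly filtered for this outcome.

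Two further objections limit the weight. If the plan's phrase about single confounders means one covariate per model, only the birth weight model is distorted: a height-only model gives -13.4 to -13.9 points, and a birth-weight-only model -1.2 to -11.3 at equal gestation. The error might also be noticed, since the univariate step would show the outcome regressed on its own component.

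A reader might also infer that the adjusted analysis would reverse the direction of the effect. The documents do not support that. Rationale says only that an association with premature delivery has been postulated, and gives no size. Reversal needs an assumed gestation gap and gestational length left out of the model.

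**Conclusion.** The point holds as a minor one: an item that does not belong among the candidate covariates is on the list, and it is not excluded by name. If the list is taken literally, a true deficit of about 13.8 percentile points appears as roughly 1 to 8 at equal gestation, so the adjusted analysis would understate the association. The direction follows from the structure of the outcome. The size rests on assumed values for the CV of birth weight, the spread of gestation and the weekly weight gain, none of which the documents give.

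It would be wrong to infer that the primary result or the sample size is compromised: the Mann-Whitney-Wilcoxon test uses no covariates, and the 80% power reproduces. The consequence is confined to the sensitivity regressions. It deserves a correction because they carry all of the planned adjustment for maternal factors.

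**What to change.** Add one sentence to Statistical analysis stating that birth weight is not an eligible covariate for the birth weight percentile outcome. Keep the maternal factors in Questionnaires as candidates: smoking, alcohol, diabetes (where not already removed by the exclusion of conditions affecting fetal growth), ethnic origin, parity, and maternal height and weight. Leaving out gestational length and newborn sex, which are already built into the percentile, is optional. The p<0.2 screen need not change for this purpose. Birth weight is still collected, since the percentile needs it. There is no cost in data, sample size or power.

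### The covariate rule for the birth weight percentile regressions lets in gestational length (and, read literally, birth weight), which removes no confounding by gestation and can, under certain conditions, bias the serology coefficient in the sensitivity analyses.

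*Combined protocol and SAP*

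**What the plan says.** The Questionnaires paragraph, after its categorical factors, lists the continuous ones: birth weight, then "gestational length, maternal height and weight". The sentence begins: "Known continuous variables are birth weight, gestational length, maternal height and weight". The Statistical analysis section refers back to that paragraph: "We will also evaluate known factors that influence birth weight (see above in paragraph questionnaire) in univariate regression models for the birth weight percentile outcome". The next step concerns "Single confounders with a potential impact on the relationship between serum-status and birth weight percentile", and these "will be included in multiple linear regression models based on the univariate results", with p<0.2 as the threshold. No sentence excludes variables that arise after exposure or that enter the calculation of the outcome.

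Two other places matter:

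- Methodology, Assessments, on the data for the outcomes: "The necessary values consist of gestational age, weight and sex of the new born". The percentile is therefore built from weight, gestational age and sex.
- Project Objectives, which asks whether pregnancies in infected women "are associated with reduced birth weight, premature delivery and stillbirth of the exposed infants". Premature delivery is also listed under the secondary analyses.

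The primary analysis is an unadjusted Mann-Whitney-Wilcoxon test. The regressions are described as sensitivity analyses.

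**The concern.** A confounder must not be a consequence of the exposure. Gestational length is fixed at delivery, and the plan itself studies one form of it, premature delivery, as a possible result of infection. The same variable is thus an outcome in one analysis and a candidate adjustment variable in another.

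The usual reason for adjusting, that babies born earlier weigh less, has already been dealt with, because the percentile compares each baby with others of the same gestational age. Whatever association remains between percentile and gestation has other sources:

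- **Causes shared by early birth and poor growth.** These give a positive correlation.
- **Dating error.** The plan allows ultrasound or menstrual dating. A baby dated too old gets too low a percentile, which gives a negative correlation.
- **Misfit of the reference curve.** This can go either way.

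Conditioning on gestation then moves the serology coefficient in a direction that cannot be known in advance. A p<0.2 screen cannot tell a confounder from a consequence of exposure.

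The regressions are the plan's only covariate-adjusted look at the primary question in an observational study. A distorted coefficient could wrongly appear to contradict or support the primary result. Birth weight, in the same sentence, is the plainer defect: the percentile is calculated from it.

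**Working it through.** **1. The plan's own figure.** Inputs from the Sample size paragraph: 40 seropositive, 160 seronegative, difference 0.5 SD, two-sided 5%, t-test. The standard error of the difference is sqrt(1/40 + 1/160) = 0.177 and the noncentrality is 0.5/0.177 = 2.83. With 198 degrees of freedom the power is 80.4%, so the stated 80% is reproduced. It refers to an unadjusted two-group comparison, so the choice of covariates does not alter it.

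**2. What the screen admits.** With n=200, p<0.2 needs |t| > 1.286, that is |r| > 1.286/sqrt(198 + 1.286²) = 0.091. A weak sample correlation is enough.

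**3. Size of the bias.** Three quantities, in SD units:

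- β: the serology effect on the percentile z-score. The plan's -0.5 is used.
- γ: the shortening of gestation by infection (assumption).
- ρ: the correlation of gestation with the percentile z-score within serogroup (assumption).

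Adjusted coefficient = β - ρ × (-γ) = β + ργ. For example, -0.50 + 0.2 × 0.3 = -0.44, and -0.50 + 0.3 × 0.5 = -0.35.

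For the false-positive rate set β=0. The adjusted standard error is 0.177 × sqrt(1-ρ²) × sqrt(1 + 0.16γ²), where 0.16 = 0.2 × 0.8 is the variance of the serology indicator.

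- γ=0.5, |ρ|=0.3: standard error 0.177 × 0.954 × 1.020 = 0.172; shift 0.15/0.172 = 0.87; rejection rate P(Z > 1.09) + P(Z < -2.83) = about 14%.
- γ=0.3, |ρ|=0.2: standard error 0.177 × 0.980 × 1.007 = 0.174; shift 0.06/0.174 = 0.34; rejection rate about 6%.

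| γ | size of ρ | Estimate of -0.50, ρ positive | Estimate of -0.50, ρ negative | False positives if β=0 |
|---|---|---|---|---|
| 0.2 | 0.1 | -0.48 | -0.52 | 5-6% |
| 0.3 | 0.2 | -0.44 | -0.56 | 6-7% |
| 0.3 | 0.3 | -0.41 | -0.59 | about 8% |
| 0.5 | 0.2 | -0.40 | -0.60 | 8-9% |
| 0.5 | 0.3 | -0.35 | -0.65 | about 14% |
| 0.5 | 0 | -0.50 | -0.50 | about 5% |

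Simulation with the p<0.2 screen applied (n=200, 40 against 160) agrees with these values to within 0.01. When β is -0.50:

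- The screen keeps gestational length in 81-100% of studies for |ρ| of 0.2 to 0.3, about 34-72% for |ρ|=0.1, and 20-27% for ρ=0.
- For positive ρ, the chance that the regression detects the effect falls to about 70% (γ=0.3, ρ=0.2) or 52% (γ=0.5, ρ=0.3).
- Coverage of the 95% interval falls to about 86% at the most severe setting.

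**4. Cross-check with a different model.** Let an unmeasured common cause load equally on gestation and percentile, with γ=0.5. A loading of 0.3 implies ρ=0.09 and gives -0.46. A loading of 0.5 implies ρ=0.25 and gives -0.37. With neither a common cause nor residual dependence, the coefficient stays at -0.50. If instead the percentile itself falls by 0.2 SD per SD of shorter gestation, the total effect is -0.60 and adjustment returns -0.50, losing 0.5 × 0.2 = 0.10.

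**5. Birth weight as covariate.** Assume weight = 0.7 × gestation + 0.7 × percentile z-score. The unadjusted effect is about -14 percentile points. Adjusting for weight gives about -7 (γ=0), -4 (γ=0.2) or 0 (γ=0.5). Adding gestational length as well gives about 0 in all three cases.

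**The case against.** The case against has several parts.

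- **The bias is conditional.** It needs both a serology effect on gestation and a residual correlation. Because the percentile already uses gestational age, the main path from short gestation to low weight is largely removed by construction. This stands. A reader might infer that adjusting for gestational length necessarily biases the result; the documents do not support that.
- **The protocol does not formally hypothesise shorter gestation.** The stated hypothesis is reduced birth weight. A link with premature delivery is reported as postulated, with more data needed, and is tested exploratively. This stands too.
- **The reach is limited.** The primary test and sample size are untouched, and the regressions were never powered. At the milder settings the shift of 0.06 is about a third of the standard error of 0.177. This also stands; the loss of detection in the regression is not a loss of the trial's planned power.
- **The plan speaks of confounders, so an analyst could leave out a mediator.** This stands only in part. The word comes with no rule except p<0.2, and gestational length does influence birth weight, so it fits the description of the candidates.
- **Nobody would regress the percentile on birth weight.** Probably so: the plan wants factors that influence birth weight, and the listing may be a slip. But the cross-reference covers the whole paragraph, so the text should say so.
- **Baby gender.** A reader might infer that it must come out for the same reason. It is redundant with a sex-specific percentile, but no bias has been shown from it.

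**Conclusion.** The point holds as a conditional one about the sensitivity regressions. By the plan's wording gestational length is a candidate covariate, although it is post-exposure, underlies a secondary outcome and is already built into the percentile. Including it is redundant at best. Under the assumed γ of 0.3 to 0.5 and |ρ| of 0.2 to 0.3, it shifts the serology coefficient by 0.06 to 0.15 SD in either direction, and the false-positive rate reaches 8% at the middle settings and 14% only at the extreme one. With γ=0.2 and |ρ| of 0.1 or less, the effect is negligible. Both γ and ρ are assumptions, and the calculation uses a normal z-score in place of the percentile.

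The change is still worth making: the term offers no control of confounding by gestation, and the screen keeps it most often when the correlation that produces the bias is present. On a literal reading birth weight is also a candidate, and its inclusion could remove half or all of the effect under the model in step 5.

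**What to change.** Add a sentence to the Statistical analysis section: gestational length and birth weight are not candidate covariates in any regression on the birth weight percentile. Gestational length serves only to calculate the percentile and to define premature delivery; birth weight serves only to calculate the percentile and, through it, IUGR. Removing baby gender from the candidates is optional.

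The cost is a wording change. No data collection changes, N=200 and the 80% power stay as stated, and the regression model has fewer terms to estimate.

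### Does taking 20% seropositivity, the top of the 10–20% range cited to the same references, make the stated 80% power unsound?

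*Combined protocol and SAP*

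**What the plan says.** Sample size estimates fixes the total by feasibility: "We estimated that n=200 mother-newborn pairs can be realistically ascertained within the funding period". It then sets the split, "we expect 20% of the serologic tested samples to be positive", giving about 40 positive and 160 negative mothers and citing references 13–15. On that basis, 200 "mother-newborn pairs has a power of 80% to detect a standardized mean difference in birth weight percentiles of 0.5" at a two-sided 5% level, with the method named: "planning by Student's test for 4:1 sample size ratio".

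The Rationale cites the same references for a range: "In these areas schistosomiasis has an estimated prevalence of 10-20" per cent. There the quantity is schistosomiasis prevalence in the regions migrants come from. The Questionnaires paragraph lists previous infection, previous treatment, fresh water contact and time since migration among the influences on the test result ("Factors resulting from exposition that can influence serological results are").

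Statistical analysis names a different test from the one used for planning: "The primary analysis will be a Mann-Whitney-Wilcoxon test". It adds regression models for the birth weight percentile, with adjustment for confounders of the serostatus relationship. The sentence on the secondary outcomes ends with "while reporting the respective effects size estimates and 95% confidence intervals".

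**The concern.** A range of 10–20% in one section becomes a flat 20% in another, with the same citation and no word on why the upper end was chosen. Because the total cannot grow, the number of seropositive mothers largely decides what the study can detect, and the chosen value is the most favourable in the quoted range. No power is shown for a smaller share.

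Two lesser points go with it. The power is for a t-test while the primary test is rank-based. And estimates with intervals are promised in the sentence about secondary outcomes, not expressly for the primary comparison. If few mothers were seropositive and only a p-value were reported, a non-significant result could be misread as evidence against a 0.5 SD effect.

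**Working it through.** **Inputs.** Total N = 200, standardised difference d = 0.5, two-sided α = 5%, t-test planning and a 4:1 ratio, all from Sample size estimates. The 10–20% range is from the Rationale. Shares of 15%, 25% and 30% are illustrations and are not in the documents. All 200 pairs are taken as analysable.

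**Formula.** For group sizes n₁ and n₂, the two-sample t-test has noncentrality δ = d·√(n₁n₂/N) with N − 2 = 198 degrees of freedom and critical value 1.972. Power is the probability that a noncentral t variable with parameter δ falls beyond ±1.972. For Mann-Whitney under a normal shift, both group sizes are multiplied by the asymptotic relative efficiency 3/π = 0.955.

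**The plan's own figure.** At 40 v 160, n₁n₂/N = 6400/200 = 32, so δ = 0.5 × √32 = 2.828 and power is 80.4%. The stated 80% is reproduced. A one-sided test would give 88.0%, so the two-sided calculation is the one that was used.

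**Other shares, N = 200, d = 0.5.**

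| Seropositive | Split | δ | t-test | Mann-Whitney |
|---|---|---|---|---|
| 10% | 20 v 180 | 0.5√18 = 2.121 | 56.0% | 54.1% |
| 15% | 30 v 170 | 0.5√25.5 = 2.525 | 71.0% | 69.0% |
| 20% | 40 v 160 | 0.5√32 = 2.828 | 80.4% | 78.5% |
| 25% | 50 v 150 | 0.5√37.5 = 3.062 | 86.1% | 84.5% |
| 30% | 60 v 140 | 0.5√42 = 3.240 | 89.7% | 88.3% |

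A simulation of 20,000 runs with normal data gave Mann-Whitney power of 78.2% at 40 v 160, 68.1% at 30 v 170 and 54.1% at 20 v 180, in line with the approximation. Like for like, going from 20% to 10% seropositive costs 80.4 − 56.0 = 24.4 points by t-test, or 78.5 − 54.1 = 24.4 points by Mann-Whitney. Changing the test at 40 v 160 costs 80.4 − 78.5 = 1.9 points.

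**What a larger sample would take.** By t-test, 80% power at 10% seropositive needs about 351 pairs, against the 200 the plan regards as realistic. With 200 pairs, the difference detectable with 80% power is about 0.66 SD at 20 v 180 and 0.50 SD at 40 v 160.

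**Interval width.** The half-width of a 95% interval for a mean difference in SD units is 1.972·√(1/n₁ + 1/n₂). At 40 v 160 this is 1.972 × 0.1768 = 0.349; at 20 v 180 it is 1.972 × 0.2357 = 0.465. Dividing by √(3/π) = 0.977 for a rank-based shift gives 0.357 and 0.476. For an invented observed difference of −0.1 SD, the lower limits would be −0.457 and −0.576. The first excludes −0.5 and the second does not. The interval therefore shows by itself how informative a null result is, whatever was assumed at planning.

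**The case for a change.** The strongest case for a change is that the dependence on the seropositive share is real and steep, while the remedy is only a sentence. Even a 15% share costs about 9 points. Reference 13, by its title, is a seroprevalence study, so serological data are among the sources cited for the 10–20%. If prevalence and seropositivity are to be distinguished, the plan could have said how it got from one to the other. All of this is fair, and a line of explanation would be good reporting.

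It does not show the 80% to be wrong, for three reasons. First, the figure is tied to an explicit split and an explicit test, so any reader can see the condition and recompute it. Second, 20% lies inside the quoted range, and the two percentages measure different things. One is prevalence in regions of origin. The other is antibody positivity among women who must all come from WHO-defined endemic areas, and the plan itself names past infection and past treatment as influences on serology. The true share could therefore lie above 20% as well as below it, and power would then exceed 80%. Third, the cited sources are not available here, so the choice cannot be called unsupported; it has a citation but no stated argument for the upper end.

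On the interval, it is true that none is expressly promised for the primary comparison. But the planned regression gives a serostatus coefficient with an interval from the same data, and analysts would report an estimate beside the primary test as a matter of course. A Hodges-Lehmann shift would also serve. It would need each birth weight converted to a z-score for gestational age and sex first, because a difference between percentiles has no single z-score equivalent.

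**Conclusion.** No change is needed. The stated 80% is correct for Student's t-test at 40 v 160 (80.4%) and about 1.5 to 2 points high for the Mann-Whitney test, which does not make the statement wrong. Power would be about 54–56% at 10% seropositive and about 85–86% at 25%. Neither share is a planning value in the documents. With the total fixed at 200 by feasibility, explaining the 20% or tabulating other shares would leave the sample, the test and the conclusions as they are. The observed split and the interval around the estimate will show at the end what was detectable. The missing interval for the primary comparison is a detail analysts supply from analyses already planned. These figures assume 200 analysable pairs, a 0.5 SD shift on a normal scale and no losses.
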